3. OBJECTIVES, ESTIMANDS AND ENDPOINTS

Objectives	Endpoints
Primary	

 To assess the efficacy of PF-04965842 compared with placebo when co-administered with background medicated topical therapy in adolescent participants 12 to <18 years of age with moderate-to-severe AD. 	
Co-primary endpoints
 
 Response based on the Investigator's Global Assessment (IGA) score of clear (0) or almost clear (1) (on a 5 point scale) and a reduction from baseline of ≥ 2 points at Week 12; Response based on the Eczema Area and Severity Index $\geq 75\%$ improvement from baseline (EASI-75) response at Week 12.
Secondary	

 To evaluate the effect of PF-04965842 co-administered with background medicated topical therapy on additional efficacy endpoints and patient reported outcomes over time in adolescent participants 12 to <18 years of age with moderate-to-severe AD. 	
Key Secondary Endpoints
 
 Response based on at least 4 points improvement in the Peak Pruritus NRS from baseline at Weeks 2, 4, and 12; Change from baseline in Pruritus and Symptoms Assessment for Atopic Dermatitis (PSAAD) total score at Week 12. 
Secondary Efficacy Endpoints
 
 Response based on at least 4 points improvement in the Peak Pruritus NRS from baseline at all scheduled time points other than Weeks 2, 4 and 12; Time to achieve at least 4 points improvement in the Peak Pruritus NRS from baseline by Day 15; Response based on the EASI-75 at all scheduled time points except Week 12; Response based on the IGA of clear

090177e19618b8f7\Approved\Approved On: 25-Jan-2021 08:51 (GMT)

090177e19618b8f7\Approved\Approved On: 25-Jan-2021 08:51 (GMT)

Objectives	Endpoints

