9.2. Sample Size Determination

A total sample of 225 participants, with 75 participants randomized to PF-04965842 200 mg QD, 75 participants randomized to PF-04965842 100 mg QD, 75 participants randomized to matching placebo (1:1:1 randomization) is planned. This would provide at least 80% power to detect a difference of at least 20% in IGA response rate between either dose of PF-04965842 and placebo, assuming the placebo response rate is 12% at Week 12. This will also provide at least 96% power to detect a difference of at least 30% in EASI-75 response

rate between either dose of PF-04965842 and placebo, assuming the placebo response rate is 23% at Week 12.

For a given dose (PF-04965842 200 mg QD or 100 mg QD), both co-primary endpoints must achieve statistical significance to meet the primary objective.

The Type-I error rate is set at 5% (two-sided). The familywise Type-I error rate (for testing the co-primary and key secondary endpoints) will be strongly controlled at 5% using a closed-testing method based on a sequential, iterative Bonferroni-type approach as outlined below.

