5. GENERAL METHODOLOGY AND CONVENTIONS

5.1. Hypotheses and Decision Rules

PF-04965842 200 mg QD will be declared superior to placebo if the null hypothesis of no difference between PF-04965842 200 mg QD versus placebo for **both** co-primary endpoints is rejected at the 5% significance level. Similarly, PF-04965842 100 mg QD will be declared superior to placebo if the null hypothesis of no difference between PF-04965842 100 mg QD versus placebo for **both** co-primary endpoints is rejected at the significance level specified below.

[figure not shown]
The familywise Type-I error rate for assessing the co-primary and key secondary endpoints will be strongly controlled at 5% (2-sided) using a sequential, Bonferroni-based iterative multiple testing procedure.

The procedure will first assess the co-primary endpoints (IGA and EASI-75 at Week 12 for 200 mg QD vs placebo) at the 5% level. If this hypothesis is not rejected, then all subsequent hypotheses will not be considered statistically significant. If this hypothesis is rejected, then assessing for statistical significance will continue as follows:

- The hypothesis for severity of pruritus (Peak Pruritus NRS4) 200 mg QD vs placebo at Week 2 will be assessed at the 2.5% level. If this hypothesis is rejected, then the unused alpha level of 2.5% will be passed on to the assessment for the key secondary endpoints and the co-primary endpoints for 100 mg QD vs placebo, in the order specified in Sequence A at a 5% significance level (see figure below). All subsequent hypotheses from any point where a hypothesis cannot be rejected will not be considered statistically significant.

- If the hypothesis for severity of pruritus (Peak Pruritus NRS4) 200 mg QD vs placebo at Week 2) is not rejected at the 2.5% level, then the hypotheses for the key secondary endpoints and the co-primary endpoints for 100 mg QD vs placebo, in the order specified in Sequence A will be assessed at a 2.5% significance level (see figure below). If all hypotheses in this sequence are rejected, then the unused alpha level of 2.5% will be passed on to the assessment of the hypothesis for severity of pruritus (200 mg QD vs placebo) at Week 2 at the 5% level. All subsequent hypotheses from any point where a hypothesis cannot be rejected will not be considered statistically significant.

Figure 2. Schematic for Multiple Testing Procedure

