5.2.1. Analyses for Binary Endpoints

Binary data at each scheduled visit will generally be analyzed by two approaches: (1) the test of hypothesis (and the p-value) of no difference between two treatment groups will be conducted by the Cochran-Mantel-Haenszel (CMH) statistic adjusting for baseline disease severity (IGA = 3 or IGA = 4); p-values from the CMH statistic will be used to test the hypothesis of no difference in binary responses between two treatment groups; and (2) the proportion of responders in each treatment group will be reported and differences between two treatment groups will be summarized by the weighted difference and its 95% confidence interval obtained by normal approximation. The difference in proportions will be calculated within each randomization stratum. The final estimate of the difference in proportions will be a weighted average of these stratum-specific estimates using CMH weights. The CMH weight w_k for stratum k ($k = 1, 2$) is given by,

$$w_k = \frac{\frac{n_{ik} n_{ck}}{n_{ik} + n_{ck}}}{\sum_{j=1}^2 \frac{n_{ij} n_{cj}}{n_{ij} + n_{cj}}}$$

where n refers to sample size, the subscript c refers to a comparator group (eg, placebo) and the subscript i refers to a test group (eg, an active treatment group). The difference is estimated as $\hat{d} = \sum_{k=1}^2 w_k (\hat{p}_{ik} - \hat{p}_{ck})$, where \hat{p} refers to the estimated proportion.

Two-sided 95% confidence intervals for the difference (based on a normal approximation) are formed by:

$$\hat{d} \pm 1.96 \sqrt{\sum_{k=1}^2 w_k^2 \left(\frac{\hat{p}_{ik}(1 - \hat{p}_{ik})}{n_{ik}} + \frac{\hat{p}_{ck}(1 - \hat{p}_{ck})}{n_{ck}} \right)}$$

In the above formula, the standard error is $\sqrt{\sum_{k=1}^2 w_k^2 \left(\frac{\hat{p}_{ik}(1 - \hat{p}_{ik})}{n_{ik}} + \frac{\hat{p}_{ck}(1 - \hat{p}_{ck})}{n_{ck}} \right)}$. When the number of responders is zero ($x = 0$), then \hat{p} will be replaced by $0.5/(n + 1)$.

The 95% confidence interval for the response rate in each treatment group will also be provided using Wald normal approximation (or the Clopper-Pearson exact method when there are no or all responders in one group).

For the Immunogenicity Sub study, the Clopper-Pearson exact method will be used to compute the associated 95% confidence interval for each treatment, while unconditional exact method proposed by Chan and Zhang will be used to compute the difference in proportions.

090177e19618b8f5\Approved\Approved On: 25-Jan-2021 08:47 (GMT)

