5.2.3. Analyses of Longitudinal Continuous Data

Mixed-effect, repeated measures (MMRM) models will be used. The fixed effects of treatment, visit, treatment-by-visit interaction and baseline disease severity will be included. Visit will be modeled as a categorical covariate. Unstructured covariance matrix will be assumed for the model errors. Compound symmetry covariance matrix will be used if the model with unstructured variance covariance doesn't converge.

When modeling the change from baseline values, the variable for visit will start with the first post-baseline visit, and the actual baseline value will be included as a covariate. At each visit, estimates of least square mean (LSM) values and the LSM differences between treatment groups will be derived from the model. The corresponding p-values and 95% confidence intervals will also be derived from the model. In the model all patients with baseline data are used for estimating baseline covariate effects and adjusting LS means.

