6.2. Secondary Endpoint(s)

6.2.1. Key Secondary Endpoint - Weeks 2, 4, and 12 Peak Pruritus NRS4 Response

- Estimand strategy: Composite, Estimand 1 (Section 2.1.1).
- Analysis set: FAS (Section 4).
- Analysis methodology: CMH and normal approximation in Section 5.2.1. Participants must have baseline PP-NRS ≥ 4 to be included in the analysis.
- Intercurrent events and missing data: The intercurrent event is captured through the variable definition; for participants who drop out for any reason, the response will be defined as “non-responsive” after that point.
- The number of participants, number and percent of response at each specified timepoints along with the 95% confidence interval by normal approximation will be presented for each treatment arm.
- The CMH test p-value, the estimate of the difference in proportions of response at each specified timepoints along with the corresponding 95% confidence interval by CMH normal approximation will be presented for each PF-04965842 dose group versus placebo.

6.2.2. Key Secondary Endpoint - Change from Baseline in PSAAD at Week 12

- Estimand strategy: Hypothetical, Estimand 2 (Section 2.1.2).
- Analysis set: FAS (Section 4). Participants must have observed baseline measure to be included in the analysis.
- Analysis methodology: MMRM in Section 5.2.3 including change from baseline data for each Week from Weeks 1 – 12.
- Intercurrent events and missing data: All data collected will be utilized; a simple average of the available values recorded within a week will be used for the analysis as a weekly measure; if there’s no available values recorded within a week, PSAAD for the week is missing and will not be used for analysis.
- Number of participants included in the analysis will be presented for each treatment arm.
- The least square mean (LSM) of change from baseline in PSAAD along with the corresponding 95% confidence interval will be presented for each treatment arm at each Week.

- The LSM difference along with the corresponding p-value and 95% confidence interval will be presented for each PF-04965842 dose group versus placebo arm at each Week.

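### The NRS4 key secondary analysis leaves out baseline Peak Pruritus NRS: a valid test, but a modest and avoidable loss of efficiency

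*Protocol*

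**What the plan says.** Protocol Section 3 lists as a key secondary endpoint "Response based on at least 4 points improvement in the Peak Pruritus NRS from baseline at Weeks 2, 4, and 12". Entry requires a baseline PP-NRS of at least 4 (Protocol 5.1, criterion 2). SAP Section 4 and SAP 6.2.1 apply the same floor to the NRS4 analysis.

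Protocol 9.4.2.2 analyses NRS4 by the method used for the co-primaries. SAP 5.2.1 defines that method as a CMH statistic "adjusting for baseline disease severity (IGA = 3 or IGA = 4", with a CMH-weighted risk difference over the same two strata. SAP 6.2.1 applies it to itch: "Analysis methodology: CMH and normal approximation in Section 5.2.1. Participants must have" a baseline of 4 or more.

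No other planned NRS4 analysis uses the baseline itch score:
- The time-to-NRS4 log-rank test is stratified by disease severity only (SAP 5.2.5, 6.2.3.2).
- The tipping-point analyses (SAP 6.1.1.2.2, 6.1.2.2.2) and the subgroup analyses (SAP 6.4) cover only the co-primaries.

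The change-from-baseline models differ. There, "the actual baseline value will be included as a covariate" (SAP 5.2.3). This covers percent change in PP-NRS (SAP 6.2.3.3) and the other key secondary, PSAAD (SAP 6.2.2).

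On alpha, once the 200 mg co-primaries succeed, Peak Pruritus NRS4 "200 mg QD vs placebo at Week 2 will be assessed at the 2.5% level" (SAP 5.1). That result decides whether Sequence A runs at 5% or 2.5%.

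**The concern.** NRS4 is an absolute fall of at least 4 points on a 0–10 scale. A participant who enters at 4 must reach 0, whereas one who enters at 8 need only reach 4. Baseline PP-NRS is therefore tied to the chance of response by the way the endpoint is built. IGA, an investigator's rating of skin signs, is at best an indirect stand-in for it.

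Leaving a prognostic baseline value out of the analysis costs precision. Chance imbalance in baseline itch also goes uncorrected, since randomisation is stratified by IGA only. At stake is some power in alpha-controlled tests within a sequence that stops at the first failure. Neither document states a power for NRS4.

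**Working it through.** **Inputs from the documents.** Protocol 9.2: "75 participants randomized to matching placebo (1:1:1 randomization) is planned"; "The Type-I error rate is set at 5% (two-sided"; and "at least 80% power to detect a difference of at least 20% in IGA response rate" from a placebo rate of 12%. For EASI-75 it states at least 96% power for 23% versus 53%. Protocol 2.2.2 gives adult Phase 2b Day 15 NRS4 rates of 69.8% (200 mg), 41.1% (100 mg) and 15.7% (placebo).

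**Step 1: the plan's own figures.** With n = 75 per arm, d = p2 − p1 and p̄ the mean of the two rates,

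power = Φ{[d − z·√(2p̄(1−p̄)/n)] / √[(p1(1−p1) + p2(1−p2))/n]}.

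- IGA, 12% vs 32%: (0.20 − 1.96 × 0.0676)/0.0656 = 1.03, so 84.8%. With continuity correction, 79.5%.
- EASI-75, 23% vs 53%: (0.30 − 1.96 × 0.0793)/0.0754 = 1.92, so 97.2%. With continuity correction, 95.9%.

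The uncorrected values satisfy both stated minimums, and the corrected ones lie within a point of them.

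**Step 2: NRS4 power as planned, no baseline itch adjustment** (z = 1.96 or 2.2414).

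| Comparison | alpha 0.05 | alpha 0.025 |
|---|---|---|
| 200 mg, 69.8% vs 15.7% | >99.9% | >99.9% |
| 100 mg, 41.1% vs 15.7% | 94.0% | 89.6% |
| 20-point effect, 35.7% vs 15.7% | 80.7% | 71.8% |

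The 20-point row is an assumption. It borrows the effect size that the protocol used for IGA.

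**Step 3: adding baseline PP-NRS, by simulation** (75 per arm, 4,000 trials per cell). Assumptions not in the documents: baseline PP-NRS 4–10 with mean 7.1 and SD 1.6, a weak link to IGA, and an odds ratio (OR) for response of 1.25, 1.5 or 2.0 per baseline point. These ORs imply placebo response at baseline 4 / 7 / 10 of 8/15/25%, 4/13/34% and 1/10/48%.

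Power, IGA-stratified CMH → standardised logistic regression with IGA and continuous baseline PP-NRS:

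| Rates | OR per point | alpha 0.05 | alpha 0.025 |
|---|---|---|---|
| 35.7% vs 15.7% | 1.25 | 81.6 → 83.2 | 72.4 → 75.5 |
| | 1.5 | 81.4 → 84.2 | 72.0 → 76.7 |
| | 2.0 | 80.7 → 87.9 | 72.7 → 82.2 |
| 41.1% vs 15.7% | 1.25 | 94.2 → 94.8 | 90.0 → 91.2 |
| | 1.5 | 94.2 → 95.6 | 90.7 → 93.0 |
| | 2.0 | 95.0 → 97.4 | 91.3 → 95.4 |

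For 35.7% vs 15.7% the gains are +1.6, +2.8 and +7.2 points at 0.05, and +3.1, +4.7 and +9.5 at 0.025. A logistic score test over the same OR range gave about 1–8 and 2–10 points. In effective sample size the gain is about 2–6% at OR 1.25–1.5 and 12–18% at OR 2.0. A separate model, in which itch falls by a proportion of its baseline, gave 2–11%.

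**Step 4: type I error at nominal 5%.** Planned CMH: 4.5–5.3% across runs. Logistic methods: 5.0–5.6%.

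**Step 5: a CMH alternative**, stratified by IGA × baseline PP-NRS (4–7 / 8–10). Type I error was 4.9–5.3%. Power at alpha 0.025 for OR 1.25, 1.5 and 2.0:
- 25% vs 45%: 62 → 62, 63 → 65, 64 → 70.
- 15.7% vs 35.7%: 73 → 72, 73 → 73, 72 → 77.

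The gain is about 0–6 points; the one small fall is within simulation error.

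**The case against.** The case for leaving the plan alone is substantial, and most of it stands.

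- **The test is valid.** CMH stratified by the randomisation factor holds its level. Nothing in the documents supports reading the omission as an error or a source of bias.
- **The Week 2 gate is not in danger.** A reader might infer that the 200 mg comparison, which sets the alpha for Sequence A, is short of power. At the Phase 2b rates its power exceeds 99.9%. Even at 60% versus a placebo rate of 25%, with alpha 0.025, it is (0.35 − 2.2414 × 0.0807)/0.0755 = 2.24, or 98.7%. Those rates are from adults, and background topical therapy may narrow the difference here, but it would have to narrow a great deal.
- **Strength of the predictor.** A reader might infer that baseline itch largely decides who can respond. Every analysed participant starts at 4 or above and so can arithmetically reach the drop. The effect is a gradient, and the documents give neither its slope nor the baseline distribution.
- **Consistency.** All binary endpoints are handled alike by design (EASI-75 also omits baseline EASI), and baseline-adjusted itch analyses exist in the MMRM models. This is a fair defence of uniformity. But those models do not test NRS4, and a fixed-point threshold is tied to baseline more directly than a percentage one.
- **Type I error.** Part of the logistic gain may be slight anti-conservatism. At 25% vs 45%, a move from 4.8% to 5.6% would by itself add about 2 points of power. It is not the main source: the score test ran at 5.0–5.2% in the runs that gave the 1–8 point gain, and the re-stratified CMH stayed near nominal and still gained 5–6 points at OR 2.0.

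**Conclusion.** The point holds as an efficiency suggestion. The alpha-controlled NRS4 analyses adjust for IGA 3 versus 4 only and leave out a baseline value that is already collected and that bears on the endpoint by construction.

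For a 20-point effect at 75 per arm, using it adds about 1–8 points of power at alpha 0.05 and 2–10 at 0.025. The upper ends need an odds ratio near 2.0 per point. At the Phase 2b Day 15 rates the gain is negligible for 200 mg and about 1–5 points for 100 mg. Everything quantitative beyond Step 2 depends on the assumed baseline distribution and prognostic strength.

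**What to change.** Before unblinding, amend Protocol 9.4.2.2 together with SAP 5.2.1 and 6.2.1, so that the two documents stay aligned:

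1. Test NRS4 at Weeks 2, 4 and 12 by a logistic-regression score test with treatment, IGA stratum and continuous baseline PP-NRS.
2. Report the standardised (marginal) risk difference with its 95% CI, and name the variance method. The effect measure remains a difference in proportions.
3. Keep the IGA-stratified CMH result as supportive.

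If a CMH test must remain primary for NRS4, stratify by IGA × baseline PP-NRS (4–7 / 8–10). This holds type I error near nominal but gains only about 0–6 points.

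The cost is wording in both documents and one changed program. No new data are needed, and the covariate cannot be missing in the analysed set because a baseline of at least 4 is already required. Two downsides should be stated: NRS4 would be analysed differently from the other binary endpoints, and the logistic test's type I error may run slightly above nominal (about 5.0–5.6%) in a chain that promises familywise control at 5%.

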4. STUDY DESIGN

4.1. Overall Design

This is a randomized, double blind, placebo controlled, parallel group, Phase 3 study to evaluate the efficacy and safety of PF-04965842 in adolescent participants 12 to <18 years of age with moderate-to-severe AD co-administered with background topical therapy. A total of approximately 225 participants will be enrolled from approximately 120 sites located globally (see Schema). The participants will be randomized 1:1:1 to receive once daily PF-04965842 at 200 mg, 100 mg, or placebo for 12 weeks. In a sub-study, up to approximately 90 participants (up to 30 in each respective study group) who have completed 8 weeks of treatment with study intervention will receive a tetanus, diphtheria and pertussis combination vaccine (Tdap) at Week 8, and will have blood samples collected for the evaluation of immunogenicity to the vaccine at Weeks 8 and 12 (see Appendix 11). The participants in the immunogenicity sub-study will complete all other protocol-specified procedures in the main study.

Qualified participants completing 12-week treatment with study intervention will have the option to enter the long-term extension (LTE) study B7451015. Participants discontinuing early from the study will undergo a 4-week follow-up.

Participants who have chronic moderate-to-severe AD as defined per the inclusion criteria will be enrolled in this study. Investigators, participants, and the sponsor study team will be blinded as to treatment group assignment. Prior to any study procedure the informed consent including any required assent will be obtained at the screening visit. Parent(s)/legal guardian will provide supplementary or sole written consent and minor children will provide assent, according to local regulations and rules regarding ability to give assent and consent.

Participants will be screened within 28 days prior to the first dose of study intervention to confirm study eligibility. During the screening period, treatments for AD will be washed out, as applicable, according to eligibility requirements. Eligible participants must have a documented history, within 6 months of the screening visit, of inadequate response to treatment with medicated topical therapy, or must have required systemic therapies for control of their disease. Eligible participants must meet the eligibility criteria at both screening and baseline visits. All treatments for AD must have been washed out for at least 7 days prior to Day 1. In addition, participants are required to use non-medicated topical therapy (ie, emollients) at least twice daily for the last 7 days prior to Day 1, and must also be willing and able to use standardized background medicated topical therapy, as per protocol guidelines, throughout the duration of the study. Participants who continue to meet eligibility criteria at baseline will undergo Day 1/baseline assessments and be randomized in a 1:1:1 ratio to receive 200 mg PF-04965842 (N=75) or 100 mg PF-04965842 QD (N=75) or matching placebo (N=75) from Day 1. Randomization will be stratified by baseline disease severity (moderate [IGA = 3] vs. severe [IGA = 4] AD).

4.2. Scientific Rationale for Study Design

This study is part of the global Phase 3 clinical development program investigating the safety and efficacy of PF-04965842 200 mg and 100 mg QD regimens. Medicated topical therapy is commonly used to treat AD. This study is designed to specifically evaluate PF-04965842 co-administered with background medicated topical therapy in adolescents with AD.

Global guidelines of vaccination recommend administration of various vaccines in adolescents. The effect of PF-04965842 on immunogenicity after vaccination in adolescents has not been evaluated. A sub-study is therefore added to investigate the effect of PF-04965842 on the immunogenicity to the Tdap vaccine. Findings of the sub-study will inform whether administration of PF-04965842 and Tdap would impair the immunogenicity to Tdap. Tdap is chosen due to its widespread use globally, inclusion of multiple antigens in this combination vaccine, and durable immune response after vaccination. Available literature data do not suggest an effect of the Tdap vaccine on AD disease activity or disease course. It is therefore considered suitable to conduct the immunogenicity sub-study during the main study.

4.3. Justification for Dose

Dose selection for Phase 3 was based on efficacy and safety of PF-04965842 from a dose-ranging Phase 2b study, B7451006 that evaluated a 20-fold dose range (10 mg to 200 mg QD) in adults with moderate-to-severe AD. The 200 mg QD dose is expected to provide efficacy similar to that of currently approved systemic treatments in moderate-to-severe AD, and was therefore selected as the high dose for evaluation in Phase 3 studies. An additional dose of 100 mg QD was also selected for evaluation in Phase 3, since this dose is expected to provide clinically efficacy in IGA response, while differentiating from the higher dose in terms of expected efficacy and systemic exposure. This will inform the selection of the dose with the most optimal benefit-risk. Both 100 mg and 200 mg QD doses demonstrated acceptable safety and tolerability in the Phase 2 study. There was no evidence of dose-dependent changes in safety endpoints such as serious infections or adverse events. Dose-response was evident only for changes from baseline in platelet counts. Mean platelet count decreases from baseline were observed with a nadir at Week 4. At Week 4 the mean platelet count and the 90% confidence interval (CI) were within the normal reference range for the 100 mg dose and 200 mg dose. The mean platelet counts increased towards baseline after Week 4. One (1) PF-04965842 treated subject with an adverse event (AE) of thrombocytopenia, had a value less than 0.5 x lower limit of normal. There were no reported adverse clinical effects potentially associated with reduced platelet counts, such as bleeding events, observed in the Phase 2 study. Further details are available in the IB.

The emerging efficacy and safety data in this study will be monitored periodically by E-DMC to ensure acceptable benefit-risk for this patient population.

